## 13.6 Exploratory Objectives

There are two exploratory objectives for this study: (1) Assess the impact of EGFRvIII expression on OS and PFS, and (2) Describe patient-reported quality of life outcomes (PROs).

Within each cohort, dose level, and EGFRvIII expression group, Kaplan-Meier curves will be used to describe OS/PFS and to estimate median OS/PFS. For each cohort, Cox proportional hazards model will be used to examine the joint effect of dose and EGFRvIII expression on PFS/OS.

Descriptive statistics (e.g. means and standard deviations) will be used to summarize each quality of life subscale at each follow-up assessment. These statistics will be generated for each cohort and dose level.

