## 6 OBJECTIVES AND ENDPOINTS

	Objective	Endpoint	Analysis
Primary	Assess the activity of Sym004 in patients with recurrent glioblastoma that are either non-bevacizumab failures (Cohort 1) or who have previously failed bevacizumab (Cohort 2)	The percentage of subjects who remain alive and progression free at 6 months (PFS6) at each dose level	See Section 13.4
Key Secondary	Determine the safety of Sym004 in recurrent GBM patients	The proportion of patients with grade 3, 4, or 5 treatment-related adverse events at each dose level	See Section 13.5.1
Other Secondary	Estimate response rate (RR) within two cohorts of recurrent GBM patients	Proportion of treated patients with a complete or partial response at each dose level	See Section 13.5.2
Other Secondary	Describe overall survival (OS) within two cohorts of recurrent GBM patients	Median OS at each dose level	See Section 13.5.2
Exploratory	Assess the impact of EGFRvIII expression on efficacy (OS and PFS) of Sym004	Median OS and PFS within subgroups of patients defined by EGFRvIII expression and dose level	See Section 13.6
Exploratory	Describe patient-reported quality of life outcomes (PROs)	Mean change from baseline in each Patient-Reported Outcome (PRO) subscale within each Cohort and dose level	See Section 13.6

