### 7.1.8 Quality of Life Assessments

Quality of Life will be assessed using standardized and validated questionnaires. These questionnaires include Functional Assessment of Cancer Therapy-Brain (FACT-BR) scale, Functional Assessment of Cancer Therapy-Fatigue (FACT-Fatigue) subscale, version 4, and Beck depression inventory II (BDI-II).

All quality of life assessments will be completed at baseline, prior to the start of every other cycle beginning with Cycle 3, and at the end of the study. These assessments should be completed prior to other study-related evaluations at study visits, if at all possible. If the subject is found to have progressive disease prior to beginning an even-numbered cycle, when HRQoL assessments are not conducted, they may complete these assessments at any time during the clinic visit.

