## 7.2 Rationale for Selection of Dose, Regimen, and Treatment Duration

Per the Sym004 Investigator's Brochure (v. 7.0, 10-Mar-2017), seven clinical trials have been conducted with Sym004, 3 clinical trials have been completed, and 4 clinical trials are ongoing. More than 365 patients with solid tumors have been exposed to Sym004 thus far in weekly doses of up to 12 mg/kg and in doses every other week of up to 18 mg/kg. Results thus far indicate that the 18 mg/kg every other week dosing results in substantially less issues with skin toxicity than other dosing/scheduling regimens (see Section 7.1.3 for details regarding the frequency of skin toxicities experienced with the Sym004 dosing regimens in ongoing clinical trials). A total of 17 patients have received 18 mg/kg every other week in Part E of the Sym004-01 trial.

In the current trial, interim analysis occurred after 19 patients were treated. After those 19 patients were treated at 18 mg/kg, it was observed that only two patients experienced grade 3 skin toxicity. Of those 19 patients, 16 patients came off study due to disease progression before reaching 6 months and only one patient completed six months of therapy before experiencing disease progression. Multiple EGFR-directed therapy trials have previously reported that patients who experience EGFR-directed therapy side effects (e.g. skin toxicity) are those who receive the greatest therapeutic benefit from this type of therapy. Hence, it is hypothesized that increasing the dose of Sym004 to 24 mg/kg in the current study might increase the frequency of skin toxicity, but also improve the overall tumor response to the therapy. Skin toxicities will continue to be managed according to Duke Medicine's "Guidelines for Management of Cutaneous Toxicity for Patients Receiving Epidermal Growth Factor Receptors" (see Appendix A), along with pre-medications described in Section 7.1.3.

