## 10.5 End of Treatment

The End of Treatment visit, i.e. the date of a subject's last treatment visit, should include:

- Interval history and full physical exam, including a full neurologic assessment and KPS
- Vital signs, including blood pressure and weight
- Hematology including CBC/differential
- CMP + Mg
- MRI of the brain
- Quality of life measurements (should be performed prior to other study-related evaluations at study visits, if at all possible)
- Skin toxicity assessment
- Toxicity assessment

If a subject goes off study and does not return to clinic as part of a regular study visit, not all tests listed above may be obtained as part of end of treatment, e.g. magnesium. If this occurs, only the assessments that are reasonably obtainable will be collected as part of end of treatment.

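### The quality-of-life endpoint is mean change from baseline, but Section 13.6 plans only subscale summaries at each follow-up, so the analysis does not yield the endpoint and is open to selection by dropout

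*Combined protocol and SAP*

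**What the plan says.** The objectives table in Section 6 gives the exploratory quality-of-life endpoint as "Mean change from baseline in each Patient-Reported Outcome (PRO) subscale within each Cohort and dose level" and points to Section 13.6 for the analysis. The analysis text there says that descriptive statistics, with means and standard deviations as the examples, "will be used to summarize each quality of life subscale at each follow-up assessment". It adds that this is done by cohort and dose level. It names no change score, no pairing with baseline and no handling of missing forms.

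The other relevant text is as follows.
- Section 7.1.8 schedules the forms at baseline, "prior to the start of every other cycle beginning with Cycle 3, and at the end of the study". For patients found to have progressed before an even-numbered cycle, "they may complete these assessments at any time during the clinic visit".
- Section 10.5 includes quality of life at the End of Treatment visit. If the patient does not return, "only the assessments that are reasonably obtainable will be collected as part of end of treatment".
- Sections 7.3 and 10.6 follow patients who are off study for progression and survival only.
- Section 13.4.3, on missing values and censoring, deals only with PFS6.
- Section 7.2 reports that, of the first 19 patients at 18 mg/kg, "16 patients came off study due to disease progression before reaching 6 months".

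**The concern.** There are two linked problems. First, the section that should deliver the endpoint describes a different quantity: the level of each subscale at a visit, not the change within patients. The means and SDs that 13.6 lists cannot supply the change afterwards. The SD of a change also needs the within-patient correlation, and the mean change needs the baseline scores of the same patients who attended.

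Second, in a disease with this much early progression, the patients with a form at a late visit are a selected part of those who started. A reader who sets late visit means beside the baseline mean of everyone is comparing different groups. If patients with poorer scores tend to leave first, the later means sit too high. The table could then hide a real decline or suggest a benefit that no patient had.

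**Working it through.** The documents state no SD, effect size or sample size for quality of life, so there is no planned figure to reproduce. The check has four parts. Scores are taken as oriented so that higher is better.

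**1. Endpoint against analysis.** Let B be the baseline mean of all patients, B_t the baseline mean of those with a form at visit t, and M_t their mean at visit t. The Section 6 endpoint is M_t − B_t. Section 13.6 reports M_t. Comparing M_t with B gives

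M_t − B = (M_t − B_t) + (B_t − B).

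The last bracket is zero only if attenders had the same baseline mean as everyone. The planned summaries report neither B_t nor the paired difference.

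**2. How many patients remain.** Observed at 18 mg/kg, both cohorts pooled: 16/19 = 84% off for progression before 6 months (Section 7.2). For 24 mg/kg, take the PFS6 benchmarks in 13.7.2 and the maximum sizes in 13.8.2 (36 and 29). Assume exponential PFS and forms only while progression-free, so the expected number at week w is N × PFS6^(w/26).

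| Cohort | PFS6 | Week 8 | Week 16 | Week 24 |
|---|---|---|---|---|
| 1 (N = 36) | 20% | 21.9 | 13.4 | 8.1 |
| 1 (N = 36) | 40% | 27.2 | 20.5 | 15.5 |
| 2 (N = 29) | 3% | 9.9 | 3.4 | 1.1 |
| 2 (N = 29) | 20% | 17.7 | 10.8 | 6.6 |

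For example, 36 × 0.20^(24/26) = 8.1.

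**3. Size of the shift when nobody changes (illustration).** Assume that baseline score and time on study are bivariate normal with correlation r, and that the longest-staying fraction remains. Then B_t − B, in SD units, is r times the mean of the retained upper normal tail. That mean is 0.798 for the top 50% and 1.400 for the top 20%.

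| r | 50% remain | 20% remain |
|---|---|---|
| 0.2 | 0.2 × 0.798 = 0.16 | 0.2 × 1.400 = 0.28 |
| 0.3 | 0.3 × 0.798 = 0.24 | 0.3 × 1.400 = 0.42 |
| 0.5 | 0.5 × 0.798 = 0.40 | 0.5 × 1.400 = 0.70 |

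The values of r are assumptions; the documents give none.

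**4. Direction when patients truly decline.** A simulation used 400,000 patients per scenario. It assumed a within-patient correlation of 0.7, a hazard of leaving multiplied by 1.0 to 2.0 per SD lower underlying quality of life, and a true decline of 0.20 SD per 8-week visit (0.60 SD by week 24). The week-24 visit mean minus the all-patient baseline mean was:

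| PFS6 | HR 1.25 | HR 1.5 | HR 2.0 |
|---|---|---|---|
| 40% | −0.44 | −0.33 | −0.19 |
| 20% | −0.33 | −0.14 | +0.07 |
| 3% | −0.04 | +0.31 | +0.62 |

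At HR 1.0 it was within 0.01 SD of −0.60. The mean paired change was within 0.01 SD of −0.60 in every scenario. That held only because leaving was made to depend on the underlying level. If patients leave because their scores are falling, paired change among attenders is biased as well.

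**The case against.** The strongest reply is that Section 6 defines the variable, that 13.6 lists example statistics without claiming to be exhaustive, and that one clarifying sentence would settle the matter. The objective is exploratory and descriptive, the study is not randomised, and no stopping or success rule uses quality of life. All of this is fair and bears on priority. It does not remove the mismatch, since no section names a change score as something to be summarised.

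A second reply also stands in part: patients who progress are not simply lost. The 8-weekly MRI and the forms fall at the same odd-cycle Day 1 visit (10.3), so a patient whose progression is found on that scan can still contribute there. Progressors before an even-numbered cycle may complete the forms, and there is an End of Treatment form. Suppose progression is found only at scheduled scans. The Cohort 1 week-24 contributors at PFS6 20% are then those progression-free at week 16, 13.4 of 36 rather than 8.1. At r = 0.3 the shift is about 0.31 SD rather than 0.40 SD, and about zero at week 8. Progression between scans would reduce this offset, the final form is collected only where obtainable, and 13.6 does not say how it will be summarised.

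Third, 13.6 plans no comparison of visit means with the full baseline group. That misreading would be a reader's, not a planned inference.

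**Conclusion.** The mismatch between endpoint and analysis is established from the text alone and needs no assumption. Heavy attrition is well supported by the plan's own figures, though 84% is a pooled figure for a dose now closed to enrolment and should not be taken as the rate at 24 mg/kg.

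The bias is conditional. A reader might infer that the visit means will look like improvement. The documents do not support that: they give no link between score and dropout, the shift vanishes if there is none, and in six of the nine declining scenarios above the visit mean still fell, only by too little. The supportable statement is that later means can mask a decline or suggest an improvement if patients with poorer scores leave first. The range of 0.16-0.40 SD with half remaining and 0.28-0.70 SD with 20% remaining is an illustration. It rests on assumed correlations of 0.2 to 0.5, no true change, and no forms from those who have left.

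This is a low-priority improvement. It affects how an exploratory result is read and no decision in the trial.

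**What to change.** In Section 13.6, state that for each subscale, by cohort and dose level:
- within-patient change from baseline is summarised (mean and SD) at each scheduled visit, in patients with both scores;
- each summary gives the number contributing out of those expected, and the contributors' own baseline mean;
- change at the end-of-treatment assessment is reported separately, where obtained, so that patients who progressed are represented;
- the text accompanying the results says that paired change removes differences in baseline between those who stay and those who leave, but not bias from dropout caused by falling quality of life.

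The cost is a few sentences in 13.6 and a small programming change. The forms are already scheduled, so no new assessment is needed, although some end-of-treatment forms may be missing under Section 10.5.

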## 13.7 Interim Analysis

### 13.7.1 Interim Efficacy Analysis for 18 mg/kg Sym004

Interim analyses for efficacy will not be conducted given the expected rapidity of patient accrual relative to the length of time required to observe the study's primary outcome. If a two-stage design were conducted with PFS6 as an endpoint, accrual would be suspended for up to 6 months to observe outcome for all patients within the first stage. Depending upon the cohort, accrual to both stages of the study could have been completed during that period of accrual suspension.

### 13.7.2 Interim Efficacy Analysis for 24 mg/kg Sym004

With Amendment 31, the design of the study will be modified. Within each cohort, a two-stage study design is used to assess outcome. The statistical properties of this design are provided in section 13.8.2. However, the stopping rules for each cohort are summarized below. After stage 1 enrollment is completed, accrual will be temporarily suspended while data from the first stage matures unless at that point 1 or more patients have survived 6-months progression-free.

Patients who have their dose escalated from 18 mg/kg to 24 mg/kg will not be considered in these interim efficacy analyses for 24 mg/kg Sym004.

Monitoring Rules		
	Cohort 1	Cohort 2
Statistical Hypothesis	PFS6 $\leq$ 20% vs PFS6 $\geq$ 40%	PFS6 $\leq$ 3% vs PFS6 $\geq$ 20%
Stage 1	Accrue 19 patients	Accrue 12 patients
Criteria for Accrual to Stage 2	>3 patients who live 6+ months progression-free	>0 patients who live 6+ months progression-free
Stage 2	Accrue 17 more patients	Accrue 17 more patients

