#### 13.4.2 Statistical Hypothesis, Model, and Method of Analysis

Based upon the Kaplan-Meier estimator, the proportion of patients who are alive and progression-free 6 months after initiation of Sym004 treatment will be estimated. Details about the hypothesis test that will be conducted is provided in Section 13.8.

The primary analyses will focus on the dose group to which the patient was originally assigned. No more than 2 of the patients treated initially at the 18 mg/kg dose will have their dose escalated to 24 mg/kg. Efficacy analyses will be generated with and without these patients to assess the impact of these patients with dose escalation on inferences.

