### 13.7.4 Initial Toxicity Monitoring among Patients Treated with 24 mg/kg Sym004

Given limited experience with 24 mg/kg Sym004, the first 3-6 patients will be slowly accrued and carefully monitored for unacceptable toxicity (see Section 7.1.2).

The first patient, regardless of cohort, will be treated and observed for 1 cycle before the accrual of a second patient. During this period of observation, the patient will receive at minimum 2 full doses of Sym004 and be followed until the end of Cycle 1. If the patient experiences an unacceptable adverse event (refer to Section 7.1.2), the study will be suspended and the patient's experience will be discussed with Symphogen to determine whether patient accrual should continue. Otherwise, 2 additional patients will be treated.

The second and third patient can be accrued at the same time. However, further accrual after the 3rd patient is suspended until completion of 1 cycle of therapy. After the first 3 patients have been observed, the number of patients with unacceptable toxicity will be determined.

- If none of the first 3 patients has an unacceptable toxic event, accrual will continue without further slowed accrual.
- If 2 of the first 3 patients has an unacceptable toxicity, the study will remain suspended. Results will be discussed with Symphogen with the expectation that accrual will be terminated.
- If 1 of the first 3 patients has an unacceptable toxicity, an additional 3 patients can be accrued after which accrual will be suspended until all patients have been observed for at least 1 cycle. If none of the additional 3 patients experiences an unacceptable toxicity, then accrual will resume without the requirement of staggered entry. If 1 of these 3 patients experiences an unacceptable toxicity, the study will remain suspended while a discussion occurs with Symphogen to determine if accrual is terminated.

For initial monitoring of the 24 mg/kg dose of Sym004, an unacceptable adverse event is defined as any grade 3, 4, or 5 adverse event that is definitely, possibly, or potentially related to Sym004 treatment.

Patients who have their dose escalated from 18 mg/kg to 24 mg/kg will be considered as part of this interim analyses of toxicity at the 24 mg/kg if they are among the first 3 (or 6) patients who receive Sym004 at the 24 mg/kg dose level.

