### 13.8.2 Sample Size Requirements for 24 mg/kg Sym004

Prior to Amendment 31, the original goal was to accrue 61 subjects to receive 18 mg/kg Sym004, with 36 patients in Cohort 1 and 25 in Cohort 2. After the approval of Amendment 31, no additional subjects will be enrolled at 18 mg/kg.

After Amendment 31, the effect of 24 mg/kg Sym004 treatment on PFS6 will be assessed in two cohorts with a maximum of 36 patients in Cohort 1 and 29 in Cohort 2. With Amendment 31, the design of the study will be modified. Within each cohort, either a two-stage minimax or two-stage optimal design will be used to assess PFS6. The same benchmarks that were used with 18 mg/kg Sym004 are used here with the same targeted type I and II error rates (i.e.  $\alpha = \beta = 0.1$ ).

Patients originally treated at the 18 mg/kg dose level who have their dose escalated to 24 mg/kg will not be considered in these analyses.

**Non-Bevacizumab Failures (Cohort 1):** A minimax two-stage design will test the hypothesis that the true PFS is 20% or less versus the alternative that the true PFS is 40% or greater. After testing the treatment on 19 patients in the first stage, the trial will be terminated if 3 or fewer patients live 6 months or more progression-free. Otherwise, additional patients will be accrued so a total of 36 patients will be treated. If the total number of patients living 6 months or more progression-free is less than or equal to 10, then the treatment is rejected as not worthy of further investigation in this patient population. The expected sample size of 28.26 and the probability of early termination is 0.455. The type I and II error rates are 0.086 and 0.098, respectively.

**Bevacizumab Failure (Cohort 2):** An optimal two-stage design will be used to test the hypothesis that the true PFS is 3% or less versus the alternative that the true PFS is 20% or greater. After testing the treatment on 12 patients in the first stage, the trial will be terminated if 0 patients live 6 months or more progression-free. Otherwise, the trial will continue and a total of 29 patients will be studied. If 2 or more patients live 6 months or more progression-free the treatment will be considered worthy of further investigation. The expected sample size of 21.64 and the probability of early termination is 0.561. The type I error rate is 0.038 and the type II error rate is 0.10.

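### At 24 mg/kg the pause after stage 1 is waived at 1 success in both cohorts, but Cohort 1 may open stage 2 only at more than 3 of 19

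*Combined protocol and SAP*

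**What the plan says.** Section 13.7.2 sets up a two-stage design within each cohort at 24 mg/kg. Once stage 1 is enrolled, "accrual will be temporarily suspended while data from the first stage matures unless at that point 1 or more patients have survived 6-months progression-free". This sentence applies to both cohorts alike.

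The table below it gives the criterion for accrual to stage 2 by cohort. For Cohort 1 (19 patients in stage 1, 17 in stage 2) it is ">3 patients who live 6+ months progression-free". For Cohort 2 (12, then 17) it is ">0 patients who live 6+ months progression-free".

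Section 13.8.2 says of Cohort 1 that, after 19 patients, "the trial will be terminated if 3 or fewer patients live 6 months or more progression-free", and that further patients, up to 36, are accrued otherwise. It reports: "The expected sample size of 28.26 and the probability of early termination is 0.455", with type I and II error rates of 0.086 and 0.098.

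**The concern.** One success is exactly what Cohort 2 needs to open stage 2, so there the waiver and the criterion agree. Cohort 1 needs four. If one, two or three of its patients have passed 6 months when patient 19 enters, the sentence lets enrolment run on, while the table says that stage 2 is not yet open. Patient 20 is a stage 2 patient.

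The futility stage exists to limit how many patients receive an inactive drug. Under the waiver, some may be treated in a cohort that then ends stage 1 at 3 or fewer. Staff also need a single rule when patient 19 enters, and the text gives two.

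**Working it through.** **Inputs.** Sections 13.7.2 and 13.8.2: n1 = 19, stop at 3 or fewer, n = 36, null and alternative PFS6 of 20% and 40%. The Cohort 1 accrual rate at 24 mg/kg is not in the documents, so a range is assumed.

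**The plan's own figures.** With X the number of successes among 19 at p = 0.20:

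- P(X ≤ 3) = 0.0144 + 0.0685 + 0.1540 + 0.2182 = 0.4551
- E[N] = 19 + 17 × (1 − 0.4551) = 28.26
- Exact two-stage error rates: 0.086 and 0.098

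All match Section 13.8.2. They belong to a design in which stage 2 opens only after 4 or more of 19.

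**How much of the early stopping is exposed.** P(1 ≤ X ≤ 3) = 0.4551 − 0.0144 = 0.441. Only a count of 0 can never trigger the waiver.

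**Exact check by number matured.** Suppose that m of the 19 have reached their 6-month time point when patient 19 enters. The chance that the pause is waived and stage 1 still ends at 3 or fewer is the sum over x = 1 to 3 of P(X_m = x) × P(Y ≤ 3 − x), with Y binomial on the other 19 − m patients. At p = 0.20 and m = 3, 5, 10, 15 this is 0.149, 0.226, 0.357, 0.420. If all 17 stage 2 patients were then treated, E[N] = 28.26 + 17 × that chance = 30.8, 32.1, 34.3, 35.4.

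**By accrual rate.** Simulation with Poisson accrual to Cohort 1 and exponential PFS at PFS6 = 20%; the waiver is checked at the 19th entry. E[N] is 28.26 plus the mean number of extra patients.

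| Cohort 1 patients per month | 1 | 1.5 | 2 |
|---|---|---|---|
| *Accrual stops at the 16th failure:* chance of stage 2 patients in a failing cohort | 27% | 28% | 23% |
| Mean extra patients; E[N] | 0.81; 29.1 | 1.22; 29.5 | 1.35; 29.6 |
| *Stops when all 19 outcomes are known:* chance | 35% | 32% | 24% |
| Mean overrun when it happens | 4 | 6 | 9 |
| Mean extra patients; E[N] | 1.46; 29.7 | 2.00; 30.3 | 2.07; 30.3 |
| *Stops 6 months after patient 19:* mean extra; E[N] | 2.29; 30.6 | 2.91; 31.2 | 2.87; 31.1 |
| *Waiver opens stage 2 outright:* E[N] | 34.7 | 33.8 | 32.4 |

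The 16th failure is the point at which 3 or fewer becomes certain, since 19 − 16 = 3. If progression is seen only at the 8-weekly MRI (Section 7.1), the first two stopping points give E[N] of 29.3 to 29.9 and 29.9 to 30.5.

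**Faster accrual.** The waiver needs patient 19 to enter at least 6 months after patient 1. At a steady pace that means 18 intervals in 6 months or more, so 3 per month or slower. With random arrivals the chance of treating stage 2 patients in a failing cohort is about 8% at 3 per month, about 1% at 4 and practically zero at 6.

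**Staggered entry.** Section 13.7.4 slows the first patients. On its longer path, "an additional 3 patients can be accrued after which accrual will be suspended until all patients have been observed for at least 1 cycle". Two scenarios, which are not bounds: with 28-day holds after patients 1 and 3, all in Cohort 1, the chance at 3, 4 and 6 per month is 12%, 5% and 0.4%. With a further hold after patient 6 it is 17%, 10% and 2%. It is smaller if early patients are in Cohort 2 or are escalated patients, who count for toxicity but not for efficacy. Of those, Section 13.4.2 says: "No more than 2 of the patients treated initially at the 18 mg/kg dose will have their dose escalated to 24 mg/kg".

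**Active drug.** At PFS6 = 40%, P(X ≤ 3) = 0.023, and the chance of an overrun is 1 to 2% at 1 to 2 per month.

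**The case against.** The strongest reply is that suspension and termination are different acts. Enrolment may run on while stage 1 matures, and the cohort still closes at 3 or fewer of 19. The two rules can be operated together, and that is why the error rates and the maximum of 36 do not move. This part stands. It does not remove the mismatch, because the table's entry is the criterion for accrual to stage 2 and the waiver allows that accrual before the criterion is met.

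The waiver may also be deliberate. Section 13.7.1 shows concern about suspending accrual for up to 6 months. That is plausible, but the plan does not say so, and it reports only the expected sample size of the design without a waiver.

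Third, accrual may be too fast for any of this to matter. Section 13.7.1 says "Depending upon the cohort, accrual to both stages of the study could have been completed during that period of accrual suspension". For Cohort 1 that would be 36 patients in 6 months, or 6 per month, where the effect is nil without staggered entry. But the statement is hedged by cohort and concerns 18 mg/kg, so it does not settle the rate here.

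A reader might infer three stronger things that the documents do not support:

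- *The type I error is inflated.* It stays at 0.086 if the rule of more than 3 of 19 is applied. Even with the interim look ignored, 11 or more of 36 gives a type I error of 0.089 and power of 0.910, both within the 0.10 targets.
- *The figure of 28.26 is a miscalculation.* It is correct for the design in Section 13.8.2 taken alone.
- *There is no stopping point.* Section 13.8.2 fixes termination once 19 patients have been tested. Only the handling of accrual before then is open.

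**Conclusion.** The concern holds as a rule that departs from the stated Cohort 1 design. Cohort 2 is not affected. The primary test is not harmed. The harm is extra exposure to an inactive drug when Cohort 1 accrues slowly: about 1 to 3 patients on average at 1 to 2 per month if the futility bound stays binding, and about 4 to 6 if the waiver is taken to open stage 2 outright. It fades at 3 per month and is close to nil at 4 or more, though staggered entry would raise it somewhat. The wording mismatch is certain. The size rests on the assumed accrual rate, the assumed stopping point, and a true PFS6 of 20%.

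**What to change.** Make the waiver in Section 13.7.2 cohort-specific, for example: *unless at that point that cohort's criterion for accrual to stage 2 has already been met (4 or more in Cohort 1; 1 or more in Cohort 2)*. This is one clause, and it keeps the expected sample size at 28.26 at any accrual rate.

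The cost is that Cohort 1 pauses more often, for up to 6 months, including when the drug works. At 2 per month and PFS6 = 40%, the pause is waived in about 26% rather than 85% of trials; at 1 per month, 74% rather than 99%.

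If the sponsor prefers to avoid the pause, keep the waiver at 1, state that termination at 3 or fewer of 19 stays binding and that accrual stops once this is certain (the 16th failure), and restate the expected sample size at the planned accrual rate. This costs no accrual time but accepts about 0.8 to 1.35 extra patients on average at 1 to 2 per month if the drug is inactive (1.1 to 1.7 if progression is seen only at the 8-weekly MRI).
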